#### **5.3.3.** Safety Evaluable Population

All randomized subjects who applied at least 1 dose of INCB018424 cream or vehicle cream will constitute the safety evaluable population. Treatment groups for this population will be determined according to the actual treatment the subject received on Day 1 regardless of assigned study drug treatment.

The safety evaluable population will be used for all safety analyses.

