#### 5.3.5. Open-Label Evaluable Population

All subjects who applied at least 1 dose of INCB018424 1.5% cream during the OL period will constitute the OL evaluable population.

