## 6.4. Exposure

For subjects in the safety population in the DB period and subjects in the OL evaluable population in the OL period, descriptive statistics will be provided by treatment group for duration of treatment, average daily dose, and total dose. Duration of treatment with INCB018424 cream or vehicle cream is defined as the number of days from Day 1 to the last record (defined in Table 2) of INCB018424 cream or vehicle cream application.

**Table 2:** Definition of Variables for Duration of Treatment

Study Period	Treatment Group a	Day 1	Last Record
--------------	------------------------------	-------	-------------

DB period	INCB018424 cream 1.5% BID 1.5% QD 0.5% QD 0.15% QD vehicle cream BID	Date of first application in DB period.	Date of last record in DB period.
OL period	INCB018424 cream 1.5% BID	Date of first application in DB period.	Date of last record in the OL period.
	INCB018424 cream 1.5% QD 0.5% QD 0.15% QD vehicle cream BID	Date of first application in OL period.	Date of last record in the OL period.

<sup>a Treatment group initially assigned or actual treatment received during the DB period.

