## 6.5. Study Drug Compliance

For subjects in the safety evaluable population, overall compliance (%) for INCB018424 cream or vehicle cream be calculated for all subjects as

Compliance (%) =  $100 \times [\text{total amount dispensed} - \text{total amount returned}] / [\text{total intended dose}]$ 

- Total amount dispensed is sum of the weights of tubes dispensed prior to the current visit.
- Total amount returned is the sum of the tubes retuned prior to and on the current visit.
- The intended dose will be based on the earliest study day of permanent discontinuation of the study drug or last study medication record in the database.

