2.7 F-BSA				
2.2.7.1		Summary	of F-	
		BSA by	Visit in	
		Open-	Label	
		Period Open evaluable	ı-label	
2.8 T-BSA		evaluable		
2.2.8.1		Cymana omy	of T-	
2.2.8.1		Summary BSA by	Visit in	
		the Open-	Label	
		Period Open		
		evaluable		
2.9 VETF				
2.2.9.1	Summary of VETF by Visit in the Open-Label Period	Open-label		
		evaluable		
2.10 PaGI	C-V	1	l	
2.2.10.1		Summary	of	
		PaGIC-V	by Visit	
	'	in the	Open-	
		Label Period	l Open-label	
		evaluable		
Safety				
3.1 Study l	Drug Exposure			
3.2.1.1	Summary of Drug Compliance in the Open-Label Period	Safety	X	
3.2.1.2	Summary of Study Drug Exposure in the Open-Label Period	Safety	X	
3.2 Advers	e Events	•	•	•
3.2.2.1	Overall Summary of Treatment-Emergent Adverse Events in	Safety	X	
	the Open-Label Period			
3.2.2.2	Summary of Treatment-Emergent Adverse Events by MedDRA System Organ Class and Preferred Term in the Open-Label Period	Safety	X	

Table No.	Title	Population	Standard	In-Text
3.2.2.3	Summary of Treatment-Emergent Adverse Events by MedDRA Preferred Term in Decreasing Order of Frequency in the Open-Label Period	Safety	X	

Maximum Severity in the Open-Label Period  2.2.5 Summary of Treatment-Related Adverse Events by MedDRA System Organ Class and Preferred Term in the Open-Label Period  2.2.6 Summary of Treatment-Related Adverse Events by MedDRA Preferred Term in Decreasing Order of Frequency in the Open-Label Period  2.2.7 Summary of Treatment-Related Adverse Events by MedDRA System Organ Class, Preferred Term, and Maximum Severity in the Open-Label Period  2.2.8 Summary of Grade 3 or 4 Treatment-Emergent Adverse	Safety Safety Safety Safety	X X X X	
MedDRA Preferred Term in Decreasing Order of Frequency in the Open-Label Period  2.2.7 Summary of Treatment-Related Adverse Events by MedDRA System Organ Class, Preferred Term, and Maximum Severity in the Open-Label Period  2.2.8 Summary of Grade 3 or 4 Treatment-Emergent Adverse	Safety	X	
MedDRA System Organ Class, Preferred Term, and Maximum Severity in the Open-Label Period  2.2.8 Summary of Grade 3 or 4 Treatment-Emergent Adverse	Safety	X	
	•		
Events by MedDRA System Organ Class and Preferred Term in the Open-Label Period	Safety	X	1
.2.2.9 Summary of Grade 3 or 4 Treatment-Related TreatmentEmergent Adverse Events by MedDRA Preferred Term in the Open-Label Period			
.2.2.10 Summary of Treatment-Emergent Adverse Events Leading to Death by MedDRA System Organ Class and Preferred Term in the Open-Label Period	Safety	X	

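### Open-label adverse event percentages are planned on all dosed subjects, including those who never applied open-label drug, and the SAP gives two populations for open-label exposure and laboratory displays

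*SAP*

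**What the plan says.** SAP 5.3.3 defines the set: "All randomized subjects who applied at least 1 dose of INCB018424 cream or vehicle cream will constitute the safety evaluable population". It then gives a rule with no limit by study period: "The safety evaluable population will be used for all safety analyses".

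SAP 5.3.5 defines a narrower set for the extension: "All subjects who applied at least 1 dose of INCB018424 1.5% cream during the OL period will constitute the OL evaluable population".

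The narrower set is used for most open-label displays: demographics (SAP 6.1.1), disposition (6.2), concomitant medication (6.6), the open-label efficacy tables and the open-label laboratory box plots (Appendix A). SAP 6.4 also uses it for exposure: "For subjects in the safety population in the DB period and subjects in the OL evaluable population in the OL period".

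The open-label safety tables in Appendix A do not use it. Table 3.2.1.2, "Summary of Study Drug Exposure in the Open-Label Period", is labelled Safety. So are Table 3.2.2.1, "Overall Summary of Treatment-Emergent Adverse Events in" the open-label period, and the compliance, laboratory and vital-sign tables. The population cell of Table 3.2.2.9 cannot be read in the available copy. SAP 8.1 to 8.4 name no open-label population that would override 5.3.3.

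**The concern.** An incidence percentage for a treatment period should be divided by the subjects who were treated in that period. SAP 8.2.2 presents adverse events as counts and percentages of subjects, so the choice of denominator changes the printed figure.

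Not every dosed subject will enter the extension. SAP 5.2 calls it optional. Protocol 4.1 requires completed baseline, Week 24 and Week 52 assessments, compliance with study medication, acceptable laboratory results and no safety concern on the investigator's part. Anyone who was dosed but did not enter is in the Safety denominator and cannot contribute an open-label event.

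The extension is the only treatment after Week 52, and Amendment 3 lengthened it partly for longer-term safety data (Protocol Appendix F). These tables are where that safety would be read. Results are shown by the arm originally assigned or received (SAP 5.2), so the dilution would differ between columns if continuation differed between arms.

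**Working it through.** The documents state no open-label percentage, so there is no figure of the plan's own to reproduce. The check is a reading of the labels followed by denominator arithmetic.

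**Step 1. Populations side by side**

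| Open-label display | SAP body | Appendix A |
|---|---|---|
| Adverse events (3.2.2.x) | 5.3.3: safety evaluable; 8.2 silent | Safety |
| Exposure (3.2.1.2) | 6.4: OL evaluable | Safety |
| Laboratory tables (3.2.3.1, 3.2.3.2) | 5.3.3: safety evaluable; 8.3 silent | Safety |
| Laboratory box plots | 5.3.3: safety evaluable; 8.3 silent | Open-label evaluable |
| Compliance (3.2.1.1) | 6.5: safety evaluable, no separate OL rule | Safety |
| Vital signs (3.2.4.x) | 5.3.3: safety evaluable; 8.4 silent | Safety |

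For adverse events the body and the appendix agree on the wider set. Exposure is contradicted between body and appendix. Laboratory displays are contradicted between tables and figures.

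**Step 2. Effect on adverse event incidence**

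Let x be the number of subjects with an open-label event, all of them entrants.

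- Percentage among those treated = x / N_OL
- Percentage as planned = x / N_safety
- Planned / treated = N_OL / N_safety

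Inputs: 150 randomized and 20% dropout by Week 24 (SAP 3.3). Assumptions: all 150 are dosed, so N_safety = 150, and nobody is lost between Week 24 and open-label entry.

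- N_OL = 150 × (1 − 0.20) = 120
- Ratio = 120 / 150 = 0.80
- Example: 12 subjects with an event give 12/120 = 10.0% but print as 12/150 = 8.0%

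The 20% is a sample-size assumption covering the first 24 weeks only. It sets neither a ceiling nor a floor on entry, so a range is needed:

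| Assumed entrants of 150 | Ratio | 10% prints as | 20% prints as |
|---|---|---|---|
| 135 | 0.90 | 9% | 18% |
| 120 | 0.80 | 8% | 16% |
| 105 | 0.70 | 7% | 14% |
| 90 | 0.60 | 6% | 12% |
| 75 | 0.50 | 5% | 10% |

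**Step 3. The other safety displays**

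- Exposure is summarized by descriptive statistics of duration, average daily dose and total dose (SAP 6.4). There is no percentage of subjects to dilute.
- Compliance is calculated as a ratio of amounts for each subject (SAP 6.5: "For subjects in the safety evaluable population, overall compliance").
- Vital signs (SAP 8.4) and numeric laboratory values (SAP 8.3.2) are summarized descriptively.
- Laboratory categories are tabulated by visit as low, normal, high or missing (SAP 8.3.2). If non-entrants are counted at open-label visits, they inflate the missing category and lower the other three. If they are dropped, nothing changes. The SAP does not say which applies.

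**The case against.** The strongest reply is that this is a loose label and not a chosen analysis. SAP 5.3.1 likewise assigns all efficacy data to the ITT population, yet the open-label efficacy tables use the open-label evaluable set, so the SAP does write general rules and narrow them elsewhere. Appendix A calls its lists guidelines. It also has other labelling slips: double-blind concomitant medication is ITT there but safety evaluable in 6.6, the double-blind laboratory box plots are ITT, and double-blind Table 3.1.2.9 has an open-label title. Finally, the tables show counts as well as percentages, and open-label disposition is reported on the open-label evaluable set, so a reader could recover the right percentage.

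Much of this stands. The label may well be unintended, and the harm is recoverable. It does not remove the defect. For efficacy, Appendix A narrows the general rule; for adverse events, it repeats it. The rule itself is in the SAP body, outside the guideline lists. A programmer who follows both would produce the diluted tables.

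A reader might go further and infer that every open-label safety percentage, including laboratory and exposure, comes out too low. The documents do not support that. Exposure, compliance, vital signs and numeric laboratory values are not counts over N; 6.4 already names the narrower set for exposure; and the laboratory categories depend on an unstated convention. Nor is the safety evaluable population confined to the double-blind period: 5.3.3 sets no period, and the difficulty is only that it is wider than the open-label set.

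**Conclusion.** The point holds for adverse event incidence. As written, the plan understates each open-label adverse event percentage by the factor N_OL/N_safety whenever any dosed subject does not enter the extension. The direction is certain under that condition, but the size is not. It is 0.80 under the stated dropout assumption with all 150 dosed and no later loss, and 0.50 to 0.90 for an assumed 75 to 135 entrants.

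The factor assumes that the tables count only events arising in the open-label period. SAP Tables 1 and 2 start the open-label clock for the original 1.5% BID arm at its first double-blind application, and SAP 8 does not say whether adverse event counting follows that. A reader might also infer that the between-arm pattern would be distorted. That needs unequal continuation, for which the documents give no figure, and no formal open-label comparison between arms is planned.

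For exposure and laboratory displays the finding is an internal contradiction over the population. Compliance and vital signs need only a consistent label.

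**What to change.** - In SAP 5.3.3, state that the safety evaluable population is used for safety analyses in the double-blind period and the OL evaluable population for safety analyses in the open-label period.
- In Appendix A, relabel Tables 3.2.1.1 to 3.2.4.6 as Open-label evaluable, consistent with SAP 6.4, 6.6 and the open-label laboratory figures. Confirm the label of Table 3.2.2.9 at the same time.

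Changing the shells alone would leave the body rule in force, so both edits are needed. The cost is SAP wording and table shells, with no new data collection. Open-label adverse event percentages will come out somewhat higher than under the present labels.

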#### 5.3.5. Open-Label Evaluable Population

All subjects who applied at least 1 dose of INCB018424 1.5% cream during the OL period will constitute the OL evaluable population.

# 6. BASELINE, EXPOSURE, AND DISPOSITION VARIABLES AND ANALYSES

Appendix A provides a list of data displays.

# 6.1. Baseline and Demographics, Physical Characteristics, and Disease History

#### 6.1.1. Demographics

The following demographics will be summarized for the ITT population in the DB period and the OL evaluable population in the OL period: age, sex, race, ethnicity, weight, height, BMI.

#### 6.1.2. Baseline Disease Characteristics

The following baseline disease characteristics will be summarized for the ITT population in the DB period:

- Years since first onset of vitiligo (< 2 years, 2-5 years, > 5 years)
- Age ( $\leq 30 \text{ or} > 30 \text{ years}$ )
- Baseline F-VASI (25% to < 50% or 50%-100%)
- Vitiligo diagnosed in childhood (No/Yes [age]: 0-5 years, 6-11 years, 12-17 years)
- Type of vitiligo (segmental/nonsegmental)
- Disease status (stable/progressive)
- Skin type (type I/II/III/IV/V/VI)
- Other autoimmune disorders (thyroid disorders/juvenile diabetes mellitus/pernicious anemia/Addison's disease/other)

- Prior therapy given for vitiligo (topical corticosteroids/vitamin D derivatives/calcineurin inhibitors/photochemotherapy/surgical techniques/excimer laser/intralesional/other)
- Current BSA involvement of the face (% of the total face)
- Current T-BSA involvement (% of the total body)

#### 6.1.3. Prior Therapy

Prior medication information for vitiligo will be used to identify medication received by subjects before enrollment into the study. Prior medications for vitiligo will be summarized by treatment group.

## **6.1.4. Medical History**

For subjects in the ITT population in the DB period, medical history will be summarized by assigned treatment group. This summary will include the number and percentage of subjects with significant medical history for each body system/organ class as documented on the eCRF.

## 6.2. Disposition of Subjects

The number and percentage of subjects who were enrolled, randomized, treated, completed the DB treatment period through Week 24 and Week 52, were treated in the OL period, completed the OL period, and/or discontinued from the study or study treatment with a primary reason for discontinuation in DB or OL treatment period will be summarized for the ITT population in the DB period and the OL evaluable population in the OL period. The number of subjects randomized/enrolled by site will also be provided by treatment group.

#### 6.3. Protocol Deviations and Violations

Protocol deviations and violations recorded on the eCRF will be presented in the subject data listings.

## 6.4. Exposure

For subjects in the safety population in the DB period and subjects in the OL evaluable population in the OL period, descriptive statistics will be provided by treatment group for duration of treatment, average daily dose, and total dose. Duration of treatment with INCB018424 cream or vehicle cream is defined as the number of days from Day 1 to the last record (defined in Table 2) of INCB018424 cream or vehicle cream application.

**Table 2:** Definition of Variables for Duration of Treatment

Study Period	Treatment Group a	Day 1	Last Record
--------------	------------------------------	-------	-------------

DB period	INCB018424 cream 1.5% BID 1.5% QD 0.5% QD 0.15% QD vehicle cream BID	Date of first application in DB period.	Date of last record in DB period.
OL period	INCB018424 cream 1.5% BID	Date of first application in DB period.	Date of last record in the OL period.
	INCB018424 cream 1.5% QD 0.5% QD 0.15% QD vehicle cream BID	Date of first application in OL period.	Date of last record in the OL period.

<sup>a Treatment group initially assigned or actual treatment received during the DB period.

## 6.5. Study Drug Compliance

For subjects in the safety evaluable population, overall compliance (%) for INCB018424 cream or vehicle cream be calculated for all subjects as

Compliance (%) =  $100 \times [\text{total amount dispensed} - \text{total amount returned}] / [\text{total intended dose}]$ 

- Total amount dispensed is sum of the weights of tubes dispensed prior to the current visit.
- Total amount returned is the sum of the tubes retuned prior to and on the current visit.
- The intended dose will be based on the earliest study day of permanent discontinuation of the study drug or last study medication record in the database.

#### 6.6. Prior and Concomitant Medication

For subjects in the safety evaluable population in the DB period and the OL evaluable population in the OL period, prior medications and concomitant medications will be coded using the WHO Drug Dictionary and summarized by WHO drug class and WHO drug term. Results will be summarized as number and percentage of subjects with prior and concomitant medications by PT and WHO drug class.

#### 7. EFFICACY

Appendix A provides a list of data displays.

#### 7.1. General Considerations

For continuous measurements, summary statistics will include sample size, mean, median, standard deviation, standard error of the mean, minimum, and maximum. For all continuous variables, both the actual value and change and/or percentage from baseline (if available) will be analyzed.

For categorical measurements, summary statistics will include sample size, frequency, and percentages.

All by-visit analyses will include the follow-up period if the data are available.

#### 7.2. Efficacy Measures

#### 7.2.1. Vitiligo Area and Severity Index

Areas affected by depigmentation due to vitiligo will be assessed using the VASI, which is a quantitative clinical tool that is analogous to the Psoriasis Area Severity Index used in psoriasis and is based on a composite estimate of the overall area of vitiligo patches at baseline and the degree of macular repigmentation within these patches over time.

In this study, F-VASI will be determined. F-VASI will be the percentage of depigmented vitiligo skin expressed as a percentage of the total area of skin on the face (100%) and estimated by the investigator using the palmar method. This will be an additional variable to be analyzed in addition to the vitiligo head/neck subscore.

The primary endpoint, which is the proportion of subjects treated with INCB018424 cream who achieve an F-VASI50 at Week 24 compared with subjects treated with vehicle cream, will be assessed using the F-VASI for the ITT population in the DB period. The percentage improvement in F-VASI score from baseline will be computed as:

100 × (Baseline F-VASI score – Observed F-VASI score) / Baseline F-VASI score.

A positive score denotes improvement, and a negative score denotes worsening.

The categorical variable F-VASI50 is defined to be equal to 1 for subjects achieving an improvement in F-VASI of at least 50% and 0 for those achieving improvement of less than 50%. A subject is said to be an F-VASI50 responder or have achieved an F-VASI50 response if F-VASI50 = 1.

The total body VASI (T-VASI) is calculated using a formula that includes contributions from all body regions (possible range, 0-100).

$$VASI =$$
 [hand units] x [Residual Depigmentation]

Briefly, the body is divided into the following 6 separate and mutually exclusive sites: head/neck, hands, upper extremities (excluding hands), trunk, lower extremities (excluding feet), and feet. The percentage of vitiligo involvement is estimated in hand units by the same investigator during the entire course of the study to eliminate variations in hand size. The degree of depigmentation for each body site was determined and estimated to the nearest of the following percentages: 0%, 10%, 25%, 50%, 75%, 90%, or 100%. At 100% depigmentation, no pigment is present; at 90%, specks of pigment are present; at 75%, the depigmented area exceeds the pigmented area; at 50%, the depigmented and pigmented area are equal; at 25%, the pigmented area exceeds the depigmented area; at 10%, only specks of depigmentation are present. The VASI is then derived by multiplying the values assessed for the vitiligo involvement by the percentage of affected skin for each body site and adding the values of all

body sites together (Hamzavi et al 2004, Dicle 2015). See Appendix C of the Protocol for the full assessment tool.

The categorical variable T-VASI50 is defined to be equal to 1 for subjects achieving an improvement in T-VASI of at least 50% and 0 for those achieving improvement in T-VASI of less than 50%. A subject is said to be a T-VASI50 responder or have achieved a T-VASI50 response if T-VASI50 = 1.

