7.6.1. Vitiligo Area and Severity Index

Areas affected by depigmentation due to vitiligo will be assessed using the VASI, which is a quantitative clinical tool that is analogous to the PASI used in psoriasis and is based on a composite estimate of the overall area of vitiligo patches at baseline and the degree of macular repigmentation within these patches over time.

In this study, F-VASI will be determined. F-VASI will be the percentage of depigmented vitiligo skin expressed as a percentage of BSA (hand unit) on the face and estimated by the investigator using the palmar or handprint (palm plus 5 digits) method. This will be an additional variable to be analyzed in addition to the vitiligo head/neck subscore.

The total body VASI is calculated using a formula that includes contributions from all body regions (possible range, 0-100).

$$VASI = \sum_{\text{all body sites}} [\text{hand units}] \times [\text{Residual Depigmentation}]$$

Briefly, the body is divided into the following 6 separate and mutually exclusive sites: head/neck, hands, upper extremities (excluding hands), trunk, lower extremities (excluding feet), and feet. The percentage of vitiligo involvement is estimated in hand units by the same investigator during the entire course of the study. Hand unit is based on subject's hand size. Investigator uses his/her hand to mimic the subject's hand size to evaluate % BSA vitiligo involvement. The degree of depigmentation for each body site was determined and estimated to

the nearest of the following percentages: 0, 10%, 25%, 50%, 75%, 90%, or 100%. At 100% depigmentation, no pigment is present; at 90%, specks of pigment are present; at 75%, the depigmented area exceeds the pigmented area; at 50%, the depigmented and pigmented area are equal; at 25%, the pigmented area exceeds the depigmented area; at 10%, only specks of depigmentation are present. The VASI is then derived by multiplying the values assessed for the vitiligo involvement by the percentage of affected skin for each body site and summing the values of all body sites together ([Hamzavi 2004](#), [Dicle 2015](#)). See [Appendix C](#) for full assessment tool.

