#### 2.3.2.2. Other Secondary Endpoints

- Assessment of the dose response on percentage change from baseline in F-VASI during the treatment periods.
- Mean and percentage change from baseline in F-VASI score during the treatment periods.
- Proportion of subjects who achieve an F-VASI50 during the treatment periods.
- Percentage change from baseline in F-BSA repigmentation during the treatment periods.
- Percentage change from baseline in T-BSA repigmentation during the treatment periods.
- Mean and percentage change from baseline in T-VASI score during the treatment periods.
- Mean and percentage change from baseline in VETF during the treatment periods.
- Proportion of subjects in each F-PhGVA and T-PhGVA category during the treatment periods.
- Proportion of subjects in each F-PaGVA and T-PaGVA category during the treatment periods.
- Proportions of subjects in each PaGIC-V category during the treatment periods.
- Proportion of subjects who report PaGIC-V of very much improved or much improved during the treatment periods.
- Times to achieve an F-VASI50 and T-VASI50.

- Times to achieve an F-PhGVA and T-PhGVA of clear or almost clear.
- Time to achieve a PaGIC-V of very much improved or much improved.
- Safety and tolerability assessed by monitoring the frequency, duration, and severity of AEs, physical examination, vital signs, and laboratory data for hematology, serum chemistry, and urinalysis.

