#### 7.2.2. Body Surface Area

At each visit, the BSA affected with vitiligo for each of 4 regions (head/neck [H], upper limbs [UL], trunk [T], and lower limbs [LL]) as a percentage of the T-BSA, as well as the face separately (depigmented area as a percent of the total area of the face) will be determined to the nearest 0.1% using, as guides, the palm plus 5 digits, with fingers tucked together and thumb tucked to the side (handprint), as 1% BSA and the thumb as 0.1% BSA.

If the subject has areas that exceed 20% that will not be treated with study drug, the BSA of these areas should be noted.

If worsening of vitiligo is present, then new areas, expansion of existing areas, or both are noted as present since the prior visit.

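### F-VASI, the primary endpoint variable, is defined on different scales in SAP and Protocol; neither states area × residual depigmentation, and the SAP baseline strata cannot be filled on the Protocol scale

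*SAP*

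**What the plan says.** **Definition of F-VASI.** SAP 7.2.1: "F-VASI will be the percentage of depigmented vitiligo skin expressed as a percentage of the total area of skin on the face (100". Protocol 7.6.1 (Version 3): "F-VASI will be the percentage of depigmented vitiligo skin expressed as a percentage of BSA (hand unit) on the face". Both say the investigator estimates it by the palmar or handprint method, and that it is analysed in addition to the head/neck subscore.

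**The product formula.** Both sections open with a general description of VASI as combining the extent of patches with how far pigment has returned inside them. Hand units × residual depigmentation then appears once in each document, introduced for the whole body: "The total body VASI (T-VASI) is calculated using a formula that includes contributions from all body regions (possible range, 0-100" (SAP 7.2.1) and "The total body VASI is calculated using a formula that includes contributions from all body regions" (Protocol 7.6.1). The grades are 0, 10, 25, 50, 75, 90 and 100%: "The degree of depigmentation for each body site was determined and estimated to the nearest of the following percentages". The sites are "head/neck, hands, upper extremities (excluding hands), trunk, lower extremities (excluding feet), and feet". The face is not a site of its own, and Protocol Appendix C has the same six rows.

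**F-BSA.** SAP 7.2.2 (and Protocol 7.6.2) measures "as well as the face separately (depigmented area as a percent of the total area of the face". It is a separate endpoint in SAP 2.3.2.2: "Percentage change from baseline in F-BSA repigmentation during the treatment periods".

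**Strata.** SAP 6.1.2 and 7.6 split baseline F-VASI into 25% to <50% and 50% to 100%.

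**Versions.** The SAP (28 JUN 2017) is based on Protocol Amendment 1 and says it stays in force for later amendments unless superseded. Only the original SAP version is listed. The F-VASI definition was updated in Protocol Amendment 2.

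**The concern.** F-VASI50 decides four of the eight tests in the graphical procedure (T11, T21, T31, T41). A 25% improvement in F-VASI decides whether a 0.15% QD subject is re-randomized at Week 24. A variable that carries this much needs one calculation rule, and three things stand in the way:

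- The two documents in force put it on different scales.
- The specific definition omits the degree component that the general description implies.
- The SAP definition reads like that of another endpoint, so it is unclear what F-VASI adds to F-BSA.

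At stake are the meaning of every reported F-VASI score, the baseline F-VASI subgroup tables and, under one possible scoring practice, responder status itself.

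**Working it through.** No stated figure in the plan depends on this definition. The sample size takes response rates (55%, 50%, 5%) as direct assumptions, so nothing there changes.

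**Step 1. Scale and percentage change.** Let H be depigmented facial skin in hand units (1 hand unit = 1% BSA, Appendix C) and A the subject's face area in % BSA, constant within a subject.

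- Protocol: F-VASI = H
- SAP: F-VASI = 100 × H/A
- F-BSA (both documents): 100 × H/A

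Percentage improvement (SAP 7.2.1) is 100 × (baseline − observed)/baseline. Putting 100 × H/A into it, the factor 100/A cancels and leaves 100 × (H₀ − H₁)/H₀. So F-VASI50 and F-VASI25 are the same under either denominator. As worded, F-VASI50 is also the same event as a 50% reduction in F-BSA.

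**Step 2. Scale and reported scores.** The score itself differs by the factor 100/A. The form in Protocol Appendix D gives head and neck together at most 9%. Taking that as an upper bound for A, the SAP score is at least 100/9 = 11.1 times the Protocol score for the same face.

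**Step 3. Strata on the Protocol scale.** A completely depigmented face scores H = A ≤ 9. Since 9 < 25, neither stratum can contain anyone. Five planned double-blind tables use categorical baseline F-VASI (2.1.1.4.2, 2.1.1.7, 2.1.2.2.2, 2.1.2.6, 2.1.3.2.2).

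The SAP scale may leave a gap too. The documents give no face area; assuming 3% to 4.5% of BSA, the entry minimum of 0.5% BSA is 0.5/3 = 16.7% down to 0.5/4.5 = 11.1% of the face, below the lowest cut of 25%.

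**Step 4. Responder status under three readings.** Assume a baseline of 1.0 hand unit, 100% depigmented (score 1.0).

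| Week 24 state | Area × grade | Pigment-free area | Outlined area |
|---|---|---|---|
| Outline unchanged, grade 50% | 1 − 1.0×0.50 = 50% | about 50% | 1 − 1.0 = 0% |
| Outline down 20%, grade 50% | 1 − 0.8×0.50 = 60% | about 60% | 1 − 0.8 = 20% |
| Outline down 40%, grade 75% | 1 − 0.6×0.75 = 55% | about 55% | 1 − 0.6 = 40% |

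The first two readings agree because the grades are themselves area shares: at 50%, depigmented and pigmented areas are equal. They differ by rounding to seven grades, which can matter close to the cut. With the outline unchanged, a patch 60% depigmented is nearest to grade 50%, giving 50% improvement by grade and 40% by area. The outlined-area reading turns all three cases into nonresponders and puts the first two below 25%.

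**The case against.** The strongest reply is that nothing is broken. Both documents speak of depigmented skin, and a half-repigmented patch has half as much of it. Involved area × grade is itself an estimate of depigmented area, so the F-VASI sentence can be read as the product in words. F-VASI is expanded in the abbreviation lists as the facial assessment of VASI, and Protocol 9.4.1.1.1 treats VASI and F-VASI together. The scale difference is version lag and cancels in the primary endpoint.

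Most of this stands, and it limits the point. Three stronger conclusions that a reader might draw are not supported:

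- *The primary endpoint ignores degree, so a half-repigmented patch counts as 0% improvement.* That needs outlined-area scoring, which neither document prescribes.
- *The denominator conflict changes who responds.* It cancels (Step 1).
- *The lack of a face row in Appendix C means the face has no scoring field.* Appendix C is the body-total form, the eCRF is not available here, and an appendix between D and F is redacted.

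What the reply does not remove is that the rule must be inferred from context, that F-VASI as worded duplicates F-BSA, and that the SAP declared itself effective for later amendments while its scale and strata no longer match the Protocol.

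**Conclusion.** The definitions conflict and should be reconciled. This is a should-fix point, and it does not show that the primary analysis is invalid.

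- **Certain from the text:** two denominators; no product stated for the face; SAP wording equivalent to F-BSA.
- **Follows by arithmetic, taking the Appendix D maximum of 9% as a bound on face area:** both SAP baseline strata are empty on the Protocol scale, and scores differ at least 11-fold between documents.
- **Conditional:** F-VASI50 and F-VASI25 change materially only if sites score outlined patches; otherwise differences are confined to rounding near the cut. The documents do not show how sites score, so the number of subjects affected cannot be computed.

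**What to change.** 1. Confirm how sites score the face, then state that one formula and one denominator in both Protocol 7.6.1 and SAP 7.2.1. If sites score facial hand units × residual depigmentation on the listed grades, write exactly that.
2. Say in SAP 7.2.2 and Protocol 7.6.2 that F-BSA is area only, and how it differs from F-VASI.
3. Restate the baseline F-VASI strata in SAP 6.1.2 and 7.6 on the chosen scale, with cuts that cover every eligible subject from the entry minimum upward.
4. If a face line is added to Appendix C, mark it as excluded from the body total. The face already lies within head/neck, and T-VASI would otherwise count it twice.

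The cost is a few sentences in each document, revised strata labels and at most one form line. No new assessment is needed, and the sample size is unaffected.
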